15.4.2.2 Analysis Methods

Continuous endpoints will be summarized by number of observations (n), mean, median, standard deviation, minimum and maximum; binary endpoints will be summarized by numerator (number of eyes meeting the endpoint), denominator, and the proportion of ITT eyes meeting the endpoint. Denominators for adverse events, slit lamp findings, and other events will be the number of eyes in the ITT set. Denominators for data such as visual acuity and other subject data that is collected at protocol-required visits will reflect the number of eyes with non-missing data in the ITT set. Summary statistics will be presented at all postoperative visits for which the endpoint data are collected. Supportive analysis will be conducted using the DI analysis set for all secondary effectiveness outcomes.

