2.1 Intention to Treat Analysis Set

The intention to treat (ITT) analysis set will be defined as the set of study eyes for which a CyPass Micro-Stent implant is attempted. The ITT analysis set will serve as the primary set for the safety and effectiveness summaries and analyses, as well as for all demographics, baseline, surgery, and study conduct summaries.

3 General Reporting Conventions

- ≠ All study eyes will receive the same treatment consisting of CyPass Micro-Stent implantation following uncomplicated cataract surgery. Therefore, summary tables will be presented for all subjects combined across all investigative centers.
- ≠ Available data at each assessment time point will be presented. No imputations will be made for missing data.
- ≠ Appropriate descriptive statistics will be computed and displayed (by assessment time point and other key variables as appropriate for both continuous and categorical variables as described below).

For continuous variables, descriptive statistics include n (number of subjects/eyes) with non-missing data, mean, standard deviation (SD), median, minimum and maximum values. The following number of decimal places will be used: mean and

median values to one more decimal place than the raw data; minimum, and maximum to the same number of decimal places as the raw data and SD to two more decimal places than the raw data.

For categorical parameters, the number and percentage of subjects/eyes within each category will be presented. The denominator for percentages will be based on the number of subjects/eyes with non-missing data appropriate for summary purposes. If a count of zero is obtained for categorical data, the zero count and percentage will still be displayed. Unless otherwise noted, percentages will be presented to one decimal place.

With the exception of the primary study endpoint, that is a one-sided test ($\alpha=0.05$), all other applicable confidence intervals (CI) will be at the $\alpha = 0.05$ (two-sided) level.

- ≠ Baseline is defined as the last assessments obtained prior to CyPass implantation surgery on Day 0.
- ≠ Change from baseline (pre-surgery) (where relevant) will only be summarized for subjects with both screening (pre-surgery) and post-op data for the relevant visit

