5.1.2 Secondary Effectiveness Endpoints

All secondary effectiveness endpoints will be evaluated at 36 months postoperatively.

≠ Mean change in IOP

- Change in IOP from baseline is defined as, for each subject,

$$Change = PostOp IOP - Baseline IOP$$

≠ Proportion of subjects with IOP reduction $\geq 20\%$ while using the same or fewer topical ocular hypotensive medications

The outcome of $\geq 20\%$ decrease in IOP from baseline up to 36 months post-operatively, while using the same or fewer topical ocular hypotensive medications, is determined as follows,

- Percent change in IOP from baseline is defined as, for each subject,

$$\text{Percent Change} = \frac{\text{PostOp IOP} - \text{Baseline IOP}}{\text{Baseline IOP}} \times 100$$

such that negative percent changes represent a favorable effect, while positive percent changes represent an unfavorable effect. Therefore, IOP response is achieved if the percent change is $\geq 20\%$ lower than baseline (i.e. the percentage change is $\leq -20\%$), while the subject is using the same or fewer topical ocular hypotensive medications compared to baseline.

- IOP response rate: Proportion of eyes meeting the effectiveness outcome is defined as the number of eyes with occurrence of $\geq 20\%$ decrease from baseline, while the subject is using the same or fewer topical ocular hypotensive medications compared to baseline, divided by the number of eyes having non-missing postoperative and baseline IOP measurements and non-missing postoperative and baseline hypotensive medication information.
- Combination ocular hypotensive medications will be counted as two medications. In particular, all combination medications will be programmatically counted as two medications:
 - ≠ Bimatoprost / Timolol
 - ≠ Brimonidine Tartrate / Timolol
 - ≠ Brinzolamide / Timolol
 - ≠ Dorzolamide HCl / Timolol Maleate
 - ≠ Latanoprost / Timolol
 - ≠ Travaprost / Timolol
 - ≠ Brinzolamide / Brimonidine Tartrate

Any subjects who are using the following oral medications will be excluded from the analysis of this endpoint.

- ≠ Acetazolamide
- ≠ Methazolamide
- ≠ Proportion of subjects who are not using ocular hypotensive medication with $\text{IOP} \geq 6 \text{ mmHg}$ and $\leq 18 \text{ mmHg}$

$$\text{Proportion} = \frac{\# \text{ of subjects not using ocular hypotensive medications having } 6 \text{ mmHg} \leq \text{IOP} \leq 18 \text{ mmHg} \text{ at the postoperative visit}}{\# \text{ of subjects in ITT set}}$$

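### SAP 5.1.2 counts eyes without a visit IOP as failures in the medication-free 6–18 mmHg proportion but drops them from the ≥20% IOP proportion, and adds an oral-medication exclusion that the protocol endpoint lacks

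*SAP*

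**What the plan says.** **Denominators.** SAP 5.1.2 defines two binary effectiveness endpoints.
- The ≥20% IOP response is the number of responding eyes "divided by the number of eyes having non-missing postoperative and baseline IOP measurements and non-missing postoperative and baseline hypotensive medication information".
- The medication-free endpoint counts subjects off hypotensive drugs whose IOP at the postoperative visit lies between 6 and 18 mmHg, divided by the number "of subjects in ITT set".

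SAP section 3 sets the general rules: "No imputations will be made for missing data", and "The denominator for percentages will be based on the number of subjects/eyes with non-missing data appropriate for summary purposes".

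Protocol 15.4.2.2 points both ways. For binary endpoints it asks for numerator, denominator "and the proportion of ITT eyes meeting the endpoint". Two sentences later it bases denominators for data gathered at scheduled visits on ITT eyes with non-missing values.

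**Oral medication.** For the ≥20% endpoint the SAP adds: "Any subjects who are using the following oral medications will be excluded from the analysis of this endpoint", naming acetazolamide and methazolamide. Protocol 8.2.1.2 mentions only topical medications for this endpoint and excludes nobody. Oral hypotensive treatment is an entry exclusion (protocol synopsis, exclusion criterion 3).

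**Timing.** SAP 5.1.2 opens with "All secondary effectiveness endpoints will be evaluated at 36 months postoperatively", then describes the ≥20% outcome as a "decrease in IOP from baseline up to 36 months post-operatively".

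**The concern.** The medication-free numerator cannot be satisfied without an IOP at the visit. Dividing by the whole ITT set therefore treats every eye without that measurement as a failure. The neighbouring endpoint leaves the same eye out. Two proportions likely to be read together would handle missing data in opposite ways, and one of them would fall as attrition rises even if outcomes among examined eyes did not change. With no hypothesis attached to these endpoints, the printed percentage is the result.

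The oral-medication rule is a separate departure. Because oral users cannot enter the study, apart from eligibility deviations, the rule mostly removes eyes for something that happens after implantation. The SAP also does not say when the use must occur to trigger removal.

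**Working it through.** **Step 1. The texts side by side.** IOP and number of hypotensive medications are collected at scheduled visits (schedule of visits, protocol section 6), so the visit-data sentence of protocol 15.4.2.2 covers both. The ≥20% denominator agrees with that sentence and with SAP section 3. The medication-free denominator agrees with neither. It agrees only with the protocol's phrase about ITT eyes.

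**Step 2. The plan's own figures.** The documents give no expected rate for either endpoint. They do give attrition of up to 20%, 450 implanted eyes and 360 with 36-month data (SAP section 7): 360 / 0.80 = 450, which reproduces.

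**Step 3. Effect of the ITT denominator.** Let p be the rate among eyes with data and m the share of ITT eyes without data.

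Printed rate = p × (1 − m); gap = p × m.

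Assumptions: ITT = 450 and p = 60%.

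| Missing m | Printed rate | Gap |
|---|---|---|
| 5% | 0.60 × 0.95 = 57% | 3 points |
| 10% | 0.60 × 0.90 = 54% (243/450) | 6 points |
| 15% | 0.60 × 0.85 = 51% | 9 points |
| 20% | 0.60 × 0.80 = 48% (216/450) | 12 points |

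At m = 20%, p = 40% prints as 32% and p = 80% as 64%.

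**Step 4. What the missing eyes could do.** If every eye were known, the rate would lie between all missing eyes failing and all succeeding.
- 10% missing: 243/450 = 54% to (243 + 45)/450 = 64%.
- 20% missing: 216/450 = 48% to (216 + 90)/450 = 68%.

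The all-ITT figure is the lower bound of this range. The non-missing figure, 60%, lies inside it.

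**Step 5. Oral users.** The documents give no frequency. Assume a share s of 1% to 5%, with 60% response in the other eyes. Excluding oral users gives 60%. Keeping them gives 0.60 × (1 − s) if none respond and 0.60 × (1 − s) + s if all respond.
- s = 1%: 59.4% to 60.4%.
- s = 5%: 57.0% to 62.0%.

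The protocol wording restricts only topical drugs, so an oral user with a sufficient fall on the same or fewer topical drugs would count as a responder. The protocol rate can therefore fall anywhere in these ranges, above or below 60%. For scale, the 95% half-width at n = 360 is 1.96 × √(0.6 × 0.4 / 360) = 5.1 points.

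**The case against.** **An explicit endpoint formula normally overrides a general convention.** SAP section 3 is headed as general, and its denominator rule leaves room for what suits the summary. ITT denominators also appear elsewhere in the SAP, for example in 6.4 and 6.5.5, and section 3 limits change-from-baseline summaries to subjects with both values, which may explain the ≥20% denominator. This stands in part: the ITT formula is not without support. But the medication-free endpoint equally needs a visit measurement, and no reason is given for treating the two differently.

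**The reader can undo the difference.** Protocol 15.4.2.2 already requires numerators and denominators, and by-visit IOP and medication summaries and an accountability table are planned. This largely stands and limits the harm. The ITT figure is also the lower one, so in a single-arm study it does not flatter the device.

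**Stronger readings that a reader might infer, and why they go too far.**
- *The oral exclusion inflates the ≥20% rate.* It does so only if those eyes would be non-responders. The protocol does not say that, so the direction is unknown.
- *A response at any visit up to month 36 counts.* The wording is loose, but the opening sentence of SAP 5.1.2 fixes month 36, and protocol 15.4.2.2 calls for summaries at each postoperative visit. By-visit assessment is the natural reading.
- *Interim rates will be deflated by eyes not yet due.* SAP 1.4 states no interim denominator, so no such figure can be derived.

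**Conclusion.** The inconsistency is in the text and should be corrected. Followed as written, SAP 5.1.2 lowers the printed medication-free rate by p × m: 3 to 12 points for 5% to 20% missing, if 60% of examined eyes succeed and the ITT set is 450. The 60% is an assumption. The 20% is the plan's upper limit, and early-exit subjects are asked to undergo the Visit 8 procedures (protocol 12.4), so the real loss may be smaller.

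The oral-medication exclusion is an undated SAP addition to the protocol endpoint. Its effect is probably small (at most 3 points either way in the example).

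Neither matter touches the primary safety test, its power or the sample size. Both endpoints are secondary and descriptive.

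**What to change.** 1. **SAP 5.1.2, denominators.** Report both proportions on eyes with non-missing data at the visit, with the all-ITT figure (missing = failure) beside each, both labelled.
2. **Protocol 15.4.2.2.** Reconcile the sentence on ITT eyes with the sentence on visit-collected data.
3. **SAP 1.4.** Use the same labels in interim summaries and limit denominators to eyes due for the visit.
4. **SAP 5.1.2, oral users.** Keep them in the denominator of the ≥20% endpoint and define oral use as use at the visit analysed. Show the rate three ways: counted as non-responders, classified by the protocol wording, and excluded.
5. **SAP 5.1.2, timing.** Define the ≥20% outcome at each postoperative visit, with 36 months as the endpoint.

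Cost: wording in two SAP sections and one protocol section, and a few table columns; no new data. The non-missing rate assumes that lost eyes resemble retained ones, which is why the all-ITT figure must stay beside it. An oral drug taken for the fellow eye could misclassify a study eye; the three-way display shows how much that could matter.

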5.1.2.1 Effectiveness Hypotheses

There are no statistical hypotheses for the secondary effectiveness endpoints; these endpoints will be summarized descriptively.

5.1.3 **Prior and Concomitant Ocular Medication Usage**

Start and stop dates of ocular hypotensive medications/treatments will be compared to the date of CyPass implantation surgery (Day 0) to allow medications/treatments to be classified as either *prior* or *concomitant*.

All medications recorded from enrollment and prior to surgery will be classified as *prior* medications. If a medication has either (1) start date before the date of surgery and a stop date on or after the date of surgery or (2) a start date on or after the date of surgery, then the medication will be classified as *concomitant*. Concomitant medications with a start date on the date of surgery will be classified as *intraoperative* medications, while concomitant medications with a start date after surgery will be classified as *postoperative* medications.

For summarization, combination ocular hypotensive medications will be counted as two medications, as specified in section 5.1.2.

Summary statistics for the average number of ocular hypotensive medications used per subject at each visit will be presented. In addition, a categorical summary of the number of ocular hypotensive medications (None, 1, 2, 3, or >3) reported at each visit will be presented. Shift tables cross tabulating hypotensive medication usage at 12, 24, and 36 months postoperatively versus baseline will be presented. Frequencies of use by medication name will be created.

6 **Safety Analysis Strategy**

6.1 **Safety Endpoints**

6.2 **Primary Safety Endpoint**

The primary endpoint is the rate of clinically relevant complications associated with CyPass Micro-Stent placement and stability as determined at 36 months.

$$\text{Rate} = \frac{\text{\# of subjects who experience clinically relevant complications associated w/ CyPass placement \& stability}}{\text{\# of subjects in ITT set}}$$

As described in the protocol, Section 8.2.2.1, the specific device-related complications included in this primary endpoint are:

- ≠ Failure to implant CyPass, defined as inability to successfully deploy or insert the CyPass.
- ≠ Clinically significant CyPass malposition, defined as CyPass positioning after deployment such that:
 - The device is not in the supraciliary space, or

- There is a clinical sequela resulting from device position including, but not limited to:
 - ≠ Secondary surgical intervention to modify device position (eg, repositioning, proximal end trimming or explantation)
 - ≠ Corneal endothelial touch by device
 - ≠ Corneal edema leading to loss of BCDVA > 2 lines at the last postoperative visit, in comparison with preoperative BCDVA
 - ≠ Progressive ECL, defined as ongoing reduction in endothelial cell count of 30% or more relative to the screening ECD value, where 'ongoing reduction in endothelial cell count' is defined as losses continuing after Visit 5 (6 Month Follow-up)
 - ≠ Erosion of device through sclera
 - ≠ Device obstruction requiring secondary surgical intervention.

6.2.1 Safety Hypothesis

The primary null hypothesis to be tested is that the observed rate of clinically relevant complications associated with CyPass Micro-Stent placement and stability is greater than or equal to the performance target rate of 7%. The corresponding alternative hypothesis to be tested is that the observed rate of complications is less than the performance target rate. These hypotheses are expressed formulaically as:

$$\begin{aligned} H_0: p_c &\geq 7\% \\ H_1: p_c &< 7\% \end{aligned}$$

where p_c is the population proportion of eyes experiencing a complication event at 36 months.

6.2.2 Analysis Methods

The primary safety hypothesis will be tested with an exact one-sided binomial test with type I error 0.05. This endpoint will be summarized by numerator (number of eyes meeting the endpoint), denominator (number of eyes in the ITT set), and the rate of ITT eyes meeting the endpoint. In addition, a summary of each individual complication type included in the primary safety endpoint (and a listing of these complications) will be provided.

Otherwise, no formal statistical hypothesis testing is planned for this study.

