15.6 Handling of Missing Data

A tipping point analysis will be performed for the primary safety endpoint.

In addition, a comparison of baseline characteristics including age, gender, race, site, and baseline unmedicated IOP will be performed between those subjects who complete Visit 8 (36 Month Follow-up) and those who do not.

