15.8 Sample Size Justification

The performance target for the primary safety endpoint is 7.0%.

An evaluation of COMPASS (TMI-09-01) data showed that through 24 months of follow-up, there were two eyes with failures to implant and eight eyes with CyPass malposition events, respectively, corresponding to the above definitions. In addition, there were four eyes with documentation of three rings visible within the first postoperative week that likely would have undergone early secondary surgical intervention due to anterior CyPass positioning under the approach documented in the Instructions for Use (IFU). Inclusion of these cases would increase the number of observed events from 10 to 14 (3.74%, 95% confidence interval: 2.1% – 6.2%). Of note, not all investigators documented the number of rings visible in the early postoperative period because this was not a study requirement (data regarding the number of rings is recorded for only 96 subjects at 1 Day and 139 subjects at 1 Week), so this number likely underestimates the number of subjects who would have been candidates for early surgical re-intervention under the new criteria described in the IFU.

Based on these considerations, the “true” event rate is assumed to be 4.0%, and the performance target is set to 7.0%. The following assumptions were used for the sample size calculation:

- ≠ Type I error = 0.05
- ≠ one-sided alternative

With a sample size of 360 subjects in the final analysis (unilateral implants only) and a performance target of 7.0%, assuming a true event rate of 4.0%, there is 80% power to reject the null hypothesis based on a one-sided alpha = 0.05-level exact test for a single proportion.

To allow for attrition over this 36-month study, a cumulative rate of up to 20% of subjects lost to follow-up is assumed, corresponding to a targeted implantation of 450 eyes in 450 subjects to achieve at least 360 eyes with 36 months of follow-up.

Annex F of ANSI standard Z80.27-2014 refers to ensuring adequate sample size so that any adverse event of a given type that occurs in the population at a rate of 1% or greater is likely to be seen in the study. With 360 subjects, there is at least 97% probability that at least one adverse event will be detected, assuming a true rate of 1.0%. There is at least 95% probability if the true rate is 0.83%.

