6.5.4	Gonioscopy and Slit Lamp Findings	16
6.5.5	Fundus Examination.....	16
6.5.6	Corneal Pachymetry	16
6.5.7	Intraocular Pressure	16
6.5.8	Visual Field Loss Mean Deviation Testing.....	17
6.5.9	Manifest Refraction	17
6.5.10	Best Corrected Visual Acuity (BCDVA)	17
6.5.11	CyPass Explantation and/or Repositioning	17
7	Sample Size and Power Calculations	17
8	References.....	18
9	Revision History	18
10	Appendix A: Schedule of Visits.....	19
11	Appendix B: Study Design	20
12	Appendix C: Data Sources.....	21
13	Appendix D: Cylinder Adjustment Converting Negative to Positive Notation....	28
14	Appendix E: Conversion of Visual Acuity Score to Snellen Values.....	28

List of Tables

Table 1-1	List of Abbreviations.....	5
Table 10-1	Schedule of Visits.....	19

Table 1-1

List of Abbreviations

ADE	Adverse device effect
AE	Adverse event
BCDVA	Best corrected distance visual acuity
CER	Clinical evaluation report
CI	Confidence interval
CRF	Case report form
CSR	Clinical study report
ICF	Informed consent form
IOP	Intraocular pressure (mmHg)
ITT	Intention to treat
logMAR	Logarithm of the Minimum Angle of Resolution
MedDRA®	Medical Dictionary for Regulatory Activities
MRSE	Manifest refraction spherical equivalent
OAG	Open angle glaucoma
OD	Right eye
OS	Left eye
OU	Both eyes
PAS	Post approval study
POAG	Primary open angle glaucoma
PT	Preferred term
SADE	Serious adverse device effect
SAE	Serious adverse event
SAP	Statistical analysis plan
SD	Standard deviation
SOC	System organ class
SSI	Secondary surgical intervention
TEAE	Treatment emergent adverse event
WHO	World Health Organization

1 Study Objectives and Design

This statistical analysis plan (SAP) describes the statistical analysis outlined in Section 15 of the study protocol (Version 4.0) along with any additional analyses planned before database lock (DBL).

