6.5.11 CyPass Explantation and/or Repositioning

A listing detailing subjects with CyPass explantation and/or repositioning will be provided. The listing will include the following variables: site-subject, age, sex, race, ethnicity, explantation or repositioning event, surgery date, study day, and reason. The data for this listing will be collected on the adverse events eCRF. Further details can be found in Appendix C: Data Sources.

7 Sample Size and Power Calculations

The performance target for the primary safety endpoint is 7.0%.

An evaluation of COMPASS (TMI-09-01) data showed that through 24 months of follow-up, there were two eyes with failures to implant and eight eyes with CyPass malposition events, respectively, corresponding to the above definitions. In addition, there were four eyes with documentation of three rings visible within the first postoperative week that likely would have undergone early secondary surgical intervention due to anterior CyPass positioning under the approach documented in the Instructions for Use (IFU). Inclusion of these cases would increase the number of observed events from 10 to 14 (3.74%, 95% confidence

interval: 2.1% – 6.2%). Of note, not all investigators documented the number of rings visible in the early postoperative period because this was not a study requirement (data regarding the number of rings is recorded for only 96 subjects at 1 Day and 139 subjects at 1 Week), so this number likely underestimates the number of subjects who would have been candidates for early surgical re-intervention under the new criteria described in the IFU.

Based on these considerations, the “true” event rate is assumed to be 4.0%, and the performance target is set to 7.0%. The following assumptions were used for the sample size calculation:

- ≠ Type I error = 0.05
- ≠ one-sided alternative

With a sample size of 360 subjects in the final analysis (unilateral implants only) and a performance target of 7.0%, assuming a true event rate of 4.0%, there is 80% power to reject the null hypothesis based on a one-sided alpha = 0.05-level exact test for a single proportion.

To allow for attrition over this 36-month study, a cumulative rate of up to 20% of subjects lost to follow-up is assumed, corresponding to a targeted implantation of 450 eyes in 450 subjects to achieve at least 360 eyes with 36 months of follow-up.

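### The primary test scores eyes that leave early as event-free to 36 months, and the SAP leaves out both missing-data analyses that Protocol 15.6 requires

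*SAP*

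**What the plan says.** SAP 6.2 defines the endpoint: "The primary endpoint is the rate of clinically relevant complications associated with CyPass Micro-Stent placement and stability as determined at 36 months". The formula there divides the subjects with a complication by all subjects in the ITT set, and 6.2.2 repeats this for the exact one-sided binomial test: "This endpoint will be summarized by numerator (number of eyes meeting the endpoint), denominator (number of eyes in the ITT set"). SAP 2.1 places every eye with an attempted implant in the ITT set, whatever its follow-up. The reporting conventions in SAP 3 add: "Available data at each assessment time point will be presented. No imputations will be made for missing data".

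The sample size in SAP 7 starts from 450 implanted eyes; "a cumulative rate of up to 20% of subjects lost to follow-up is assumed", which leaves 360 eyes with 36-month data. Under Protocol 12.4, sites should try to bring a leaver back for the Visit 8 procedures.

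On missing data, Protocol 15.6 says: "A tipping point analysis will be performed for the primary safety endpoint". It also requires "a comparison of baseline characteristics including age, gender, race, site, and baseline unmedicated IOP will be performed between those subjects who complete Visit 8" and those who do not. SAP 1 opens with "This statistical analysis plan (SAP) describes the statistical analysis outlined in Section 15 of the study protocol (Version 4.0"), yet neither analysis appears in the SAP. On attrition it offers a disposition table, a listing of discontinuation reasons and an accountability table (SAP 4.1).

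**The concern.** The parameter is the proportion of eyes with an event by 36 months. The planned estimate counts recorded events over all eyes, including eyes not followed that far. Implant failures, events before exit and findings at an early-exit visit are all counted. Anything after exit is not. In a single-arm test that succeeds on a low rate, an unseen event can only push towards success. Some components are open to this: progressive endothelial cell loss requires losses continuing after the 6-month visit, so it cannot be shown in an eye last seen before then.

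The tipping-point analysis is the protocol's own check on this. Protocol 15.6 gives it one sentence and no method, and the SAP gives it nothing. If that stays so, the method would be chosen after the data are known in an open-label study, and a marginal pass could not be told from a robust one.

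**Working it through.** **Inputs.** Null rate 7%, assumed true rate 4%, one-sided 0.05 exact binomial test, 360 eyes in the power calculation, 450 implanted, up to 20% lost (SAP 6.2.1, 6.2.2 and 7).

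**The plan's own figure.** The critical count c is the largest count with P(X ≤ c | n, 0.07) ≤ 0.05; power is P(X ≤ c | n, 0.04).

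- n = 360: c = 17, type I error 0.0499, power 0.802. The stated 80% reproduces, and 360 / 0.80 = 450.
- n = 450, the denominator actually tested: c = 22, type I error 0.0429, power 0.860 if no event is missed.

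**Effect of unseen events.** Let d be the share of eyes that exit early and f the share of leavers' events that fall after exit. If leavers have the same true rate as others, the recorded rate at a true 7% is 0.07 × (1 − d × f), and type I error is P(X ≤ 22 | 450, 0.07 × (1 − d × f)).

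The documents do not give f. Assume that exits are non-informative and that exits and later events are spread evenly over follow-up. On average half of a leaver's later events then fall after exit, so f = 0.5 × (1 − early share).

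Three early shares are used:

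- **6 of 14.** Protocol 15.8 counts 14 reference-trial events: 2 implant failures, 8 malposition events and "four eyes with documentation of three rings visible within the first postoperative week". Taking 2 + 4 = 6 as early treats all eight malpositions as late.
- **10 of 14.** This amounts to treating half of the eight malpositions as early (6 + 4 = 10).
- **80%.** This is an assumption with no source in the documents.

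| Early share | f | Type I error, 20% exits | Type I error, 10% exits |
|---|---|---|---|
| 80% | 0.100 | 5.4% | 4.8% |
| 10 of 14 | 0.143 | 6.0% | 5.1% |
| 6 of 14 | 0.286 | 8.1% | 6.0% |

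Worked case: 20% exits and 6 of 14 early give d × f = 0.0571, a recorded rate of 0.07 × 0.9429 = 0.0660, and P(X ≤ 22 | 450, 0.0660) = 0.081.

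**Where 5% is crossed.** P(X ≤ 22 | 450, p) = 0.05 at p = 0.0691, and 1 − 0.0691 / 0.07 is about 1.3%. So type I error passes 5% once about 1.3% of all events go unseen, which is about 7% of leavers' events at 20% exits and 13% at 10% exits.

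**Tipping point.** At n = 450, 23 events fail (P(X ≤ 23 | 450, 0.07) = 0.065). The number of unseen events that reverses a pass is 23 minus the recorded count: one at 22 recorded, three at 20, nine at 14.

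**The case against.** Several counter-arguments stand in part.

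- **Protocol 15.6 already covers it.** It does still bind, and it names the two groups and five variables for the baseline comparison. A reader might infer that the SAP has withdrawn these analyses; nothing says so. What is undefined is the tipping-point method.
- **The no-imputation line.** A reader might infer that it forbids a tipping-point analysis. It is a general convention about presenting available data, and a tipping point expressed as a count imputes nothing. The conflict is weak and needs only a clarifying sentence.
- **Most events may be early.** If so, the effect is small: 4.8% to 5.1% at 10% exits for the two milder scenarios. The 20% is a planning ceiling, and early-exit visits recover events up to exit. For a subject who dies, scoring no later event can be correct. Progressive endothelial loss can also first be shown at the 12-month visit, so it does not always need the last years of follow-up.
- **A larger inflation.** Assuming that no events are early gives 12.6% at 20% exits. That does not fit Protocol 15.8, where 2 of the 14 events are implant failures and 4 are first-week findings.
- **The ITT set is the protocol's own choice** (Protocol 15.5.1.2), and testing 450 rather than 360 eyes costs no power. A reader might infer that the primary test must be replaced. The documents do not support that.

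None of this changes the direction of the effect or fills the gap in the SAP.

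**Conclusion.** The concern holds in limited form, as a should-fix. Two parts are certain from the text. Follow-up time that nobody observed counts as event-free, in the direction that favours success. The SAP also omits two analyses that Protocol 15.6 requires, one of them with no method anywhere.

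The size is not certain. The scenario range of 4.8% to 8.1% for type I error rests on assumed early shares, 10% or 20% exits, and non-informative, evenly spread exits and later events. At its low end the 5% level is kept. The practical risk is a marginal pass: at 22 recorded events the conclusion has no margin, while at 14 it could absorb eight unseen events. The stated sample size arithmetic is correct.

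**What to change.** Before database lock:

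1. Put both Protocol 15.6 analyses in the SAP. Define the tipping point as the number of unseen events, among eyes without 36-month data, that reverses the conclusion (23 minus recorded events if 450 eyes). Report it beside the success claim, and state that the no-imputation convention does not apply to it.
2. Keep the exact ITT test as primary. Add, as a sensitivity analysis, a Kaplan-Meier 36-month rate with a one-sided 95% upper limit compared with 7%. Use nominal visit times, with Visit 8 as the single 36-month time point. State the non-informative censoring assumption, how deaths are handled as distinct from loss to follow-up, and the event-date rule, including for the corneal edema component judged at the last postoperative visit.

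The time scale matters because Visit 8 spans days 1050 to 1140. In simulation at a true 7%, Kaplan-Meier on nominal visit times held type I error at about 3.6% to 4.3%, where the crude test gave 5.6% to 9.6%. With a fixed day, 20% exits and 6 of 14 events early, it was about 7.0% at day 1095 and about 0.6% at day 1140.

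The cost is SAP text and a little programming, with no protocol change and no new data. The downside is that a marginal pass may be shown as not robust. Kaplan-Meier is also imperfect: in the simulations with 20% exits, type I error exceeded 5% when leavers had 1.5 or 2 times the late-event risk (5.6% or 6.8% with 6 of 14 early). It therefore belongs beside the tipping point and does not replace it.
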